Avelumab

B9991047 NON-INTERVENTIONAL STUDY PROTOCOL

Version 2.0, 3rd July 2023

NON-INTERVENTIONAL (NI) STUDY PROTOCOL

CCI

Study information

Title	A MULTI-CENTRE NON-INTERVENTIONAL STUDY TO DESCRIBE THE EARLY CLINICAL EXPERIENCE OF AVELUMAB USED AS MONOTHERAPY FOR THE FIRST-LINE MAINTENANCE TREATMENT OF ADULT PATIENTS WITH LOCALLY ADVANCED OR METASTATIC UROTHELIAL CARCINOMA WHO ARE PROGRESSION-FREE FOLLOWING PLATINUM-BASED CHEMOTHERAPY
Protocol number	B9991047
Protocol version identifier	Version 1.0
Date	21 st July 2021
Active substance	LO1XC31
Medicinal product	Avelumab
Research question and objectives	To understand the early clinical experience of using avelumab as monotherapy for first line (1L) maintenance treatment of adult patients with locally advanced or metastatic Urothelial Carcinoma (UC) including describing the real-world overall survival (rOS) in patients who are progression-free following platinum-based chemotherapy.
Author(s)	PPD [REDACTED] [REDACTED]

2. LIST OF ABBREVIATIONS

Abbreviation	Definition
AE(s)	Adverse event(s)
AEM	Adverse event monitoring
BSC	Best supportive care
CAG	Confidentiality Advisory Group
CSA	Clinical study agreement
CSR	Clinical study report
CPS	Combined positive score
CRF	Case report form
EAMS	Early Access to Medicines Scheme
EC	European Commission
ECOG	Eastern Cooperative Oncology Group
eCRF	Electronic case report form
EDC	Electronic data capture
EHR	Electronic Health Record
EMA	European Medicines Agency
EU	European Union
FDA	Food and Drug Administration
HRA	Health Research Authority
IEC	Independent ethics committee
IgG1	Immunoglobulin G1

IRB	Institutional review board
IRAS	Integrated research application system
IQR	Inter-quartile range
JB100	JAVELIN Bladder 100
NHS	National Health Service
NIS	Non-interventional study
PD-L1	Programmed death-ligand 1
QMS	Quality management system
rwTTNT	Real-world time to next treatment
rwOS	Real-world overall survival
rwPFS	Real-world progression-free survival
rwTTD	Real-world time to discontinuation
REC	Research ethics committee
R&D	Research and Development
SDV	Source data verification
SACT	Systemic anti-cancer therapy
SAP	Statistical analysis plan
SOP	Standard operating procedure
TCC	Transitional cell carcinoma
UC	Urothelial carcinoma
UK	United Kingdom

USA	United States of America
YRR	Your reporting responsibilities
1L	First-line
2L	Second-line

4. ABSTRACT

Title	A multi-centre non-interventional study (NIS) to describe the early clinical experience of avelumab used as monotherapy for the first-line maintenance treatment of adult patients with locally advanced or metastatic UC who are progression-free following platinum-based chemotherapy.
--------------	---

Rationale and background	
Bladder cancer is the 11th most common cancer in the United Kingdom (UK). Patients with advanced or metastatic UC are usually offered a platinum-based chemotherapy. Avelumab is a human monoclonal antibody which, as demonstrated in the JAVELIN Bladder 100 (JB100) trial, is associated with a median overall survival gain of 7.1 months when used as maintenance therapy in combination with best supportive care (BSC) compared with BSC only. The drug has been approved by the Food and Drug Administration (FDA) and the European Medicines Agency (EMA) for monotherapy for the first-line maintenance treatment of adult patients with locally advanced or metastatic UC who are progression-free following platinum-based chemotherapy. Access to the drug has initially been facilitated by the Early Access to Medicines Scheme (EAMS) programme in the UK since September 2020. There is now a need for UK-specific early clinical and outcome data in patients treated with avelumab for this indication in routine clinical care.

Research question and objectives	
The primary objective of this study is to estimate real-world overall survival (rwOS) in a real-world cohort of patients treated with avelumab monotherapy for the first-line maintenance treatment of adult patients with locally advanced or metastatic UC who are progression-free following platinum-based chemotherapy.
 
The secondary objectives are:
 
 1. To describe the clinical and demographic characteristics of the study population 2. To estimate real-world progression-free survival (rwPFS) 3. To describe treatment characteristics of 1L anti-cancer therapies received prior to the initiation of avelumab as 1L maintenance therapy 4. To describe treatment patterns after initiation of avelumab as 1L maintenance therapy 5. To describe the adverse events (AEs) explicitly attributed to avelumab in a real-world population 6. To describe real-world all-cause associated healthcare resource burden associated with avelumab therapy

Study design	
A multi-centre NIS with both a retrospective chart review and prospective follow-up of patients conducted in selected secondary/tertiary care centres of the UK National Health Service (NHS). The study will be entirely conducted using records obtained in routine clinical care and will not involve contact with patients.
 
Confidential Advisory Group (CAG) and appropriate ethics permission will be obtained before commencing the study.

Population	
Patients must meet all the following criteria to be eligible for inclusion in the study:
 
 1. Patients with a diagnosis of locally advanced or metastatic UC, either de novo or relapsed 2. Patients received 1L platinum-based chemotherapy and had stable disease, partial response, or complete response to this treatment 3. Patients received avelumab as indicated as a monotherapy for the first-line maintenance treatment of adult patients with locally advanced or metastatic UC who are progression-free following platinum-based chemotherapy 4. Patients aged ≥ 18 years on the date that they commenced avelumab 
Patients meeting any of the following criteria will be excluded from the study:
 
 1. Patients whose hospital records are not available for review 2. Patients who are receiving an investigational medicinal product as part of a clinical trial at the time of maintenance therapy with avelumab
Variables	
Variables to be collected include:
 
Demographic and clinical characteristics of the study population, at selected time points, including:
 
 ○ Age at diagnosis and at avelumab initiation ○ Diagnostic details on UC ○ Eastern Cooperative Oncology Group (ECOG) performance status ○ Cigarette smoking history 
Treatment characteristics prior to avelumab initiation, including:
 
 ○ Systemic anti-cancer therapy (SACT) regimen received

	
○ Number of platinum-based chemotherapy cycles received since initial diagnosis○ Number of distinct platinum-based chemotherapies received○ Time from completion of 1L SACT to avelumab initiation○ Response to 1L therapy 
Treatment characteristics from avelumab initiation, including:
 
○ Duration of avelumab treatment○ Time to second-line (2L) therapy○ SACT regimen received as 2L therapy○ Number of cycles received as 2L therapy○ Time from initiation of avelumab to treatment discontinuation○ High dose systemic steroid treatment following initiation of avelumab 
Adverse events explicitly attributed to avelumab treatment:
 
○ AE diagnosis○ Outcome of AE○ Classification as either serious or non-serious AE○ Results in hospitalisation or prolongation of hospitalisation○ Is life threatening○ Resulted in death○ Persistent or significant incapacity○ Congenital anomaly/birth defect in any offspring○ Other important medical event that may require medical or surgical intervention to avoid any of the above criteria○ AEs leading to administration adjustments or discontinuation of avelumab○ AEs leading to systemic steroid treatment 
All-cause associated healthcare resource burden:
 
○ Accident and emergency visits○ Hospitalisations○ Duration of hospitalisation
--	---

Data sources	A total of 8-12 NHS centres will be selected for this study and each of them will be required to identify a minimum of 6 patients identified in sequential order from the first eligible patient treated at the site according to prespecified criteria. Data on patient and treatment characteristics as well as events and outcomes will be extracted from patient medical records and hospital charts from participating NHS sites using electronic case report forms (eCRF).
Study size	We aim to include approximately 100 patients into the study and follow them up for treatment patterns, events and endpoints in the study for up to 24 months per patient.
Data analysis	Clinical and demographic characteristics, treatment characteristics, toxicity and AEs will be analysed descriptively, where continuous variables will be described using the mean (with standard deviation) and/or the median (with inter-quartile range, IQR) and categorical variables will be described using number and percentage. rwOS, rwPFS, time to next treatment (rwTTNT) and time to discontinuation (rwTTD) will be analysed using time to event analysis. Survival curves and median survival times will be estimated using Kaplan-Meier methods.
Milestones	Study commencement: August 2021 Study completion: December 2024 Final study report: January 2025

5. AMENDMENTS AND UPDATES

Amendment number	Date	Protocol section(s) changed	Summary of amendment(s)	Reason
1	30/06/2023	All sections	Changes of mentions of Pfizer to Merck Serono, change in authorship, pharmacovigilance reporting	Change of sponsor to Merck Serono because of the Merck -Pfizer Alliance termination on Avelumab
2	30/06/2023	Section 3 – Responsible authors	Removal of Pfizer author and replacing the previous Merck Serono author with the current study lead PPD	Change of sponsor to Merck Serono because of the Merck Serono-Pfizer Alliance termination on Avelumab
3	30/06/2023	Section 4 & 6 - Milestone	Update to the data collection end date from November 2023 to June 2024 Update of report date from June 2024 until January 2025	We expect the last patient enrolled to complete 24 months follow up by end of June 2024, this will push the final study report till January 2025
4	30/06/2023	Section 10.4 – Ethical conduct	Replacing mentions of 'controlled document pertaining to Pfizer' with Merck Serono controlled documents	We will be using Merck Serono controlled documents
5	30/06/2023	Section 11	Replacing the Pfizer specific document name 'NIS Adverse Event Monitoring (AEM) Report Form'	We will be using Merck Serono's Adverse Event Report Form.

			
with 'NIS Adverse Event (AE) Report Form
 
Replacing 'Your Reporting Responsibilities Training' by 'Merck PV Responsibilities Training' or similar Merck Serono local training
	
Training reference updated to a Merck Serono one

--	--	--	--	---

6. MILESTONES

Milestone	Planned date
Completion of feasibility assessment	August 2021
Ethics approval	August 2021
Start of data collection	November 2021
End of data collection	June 2024
Interim report 1	November 2022
Study progress report 1	On the 1-year anniversary of receiving ethical approval in the UK
Final study report	January 2025

7. RATIONALE AND BACKGROUND

Urothelial carcinoma, also known as transitional cell carcinoma (TCC) arises from the transitional epithelium in the urinary system and is the most commonly occurring bladder cancer (1). Risk factors for UC include cigarette smoking, older age, being of male sex, being Caucasian, genetic susceptibility, having a family history, chronic bladder infections as well as arsenic and chemical exposure (2). Patients usually present with haematuria, difficulty urinating, pelvic pain, bone pain and unintentional weight loss (3).

There were 10,233 new incident cases of invasive bladder cancer (ICD-10 code C67) annually in the UK 2015-2017, with 5,485 deaths annually between 2016-2018. Bladder cancer is the 11th most common cancer in UK, and the 10th most common cause of cancer death in the UK. When diagnosed at its earliest stage, more than 9 in 10 (95%) people with bladder cancer will survive their disease for one year or more, compared with more than 1 in 3 (36%) people when the disease is diagnosed at the latest stage (4). Five-year age-standardised survival is 53% for all patients, ranging from 79% for stage I to 41% for stage III patient (5). Five-year survival data for stage IV patients in the UK are not available but data from the United States of America (USA) report that 5-year relative survival decreases to 37% if it has spread to regional lymph nodes, and to 6% if it has spread to a more distant site (6).

Treatment success depends on how early the patient is diagnosed and treated. In early stage UC, surgical resection is the course of action, while advanced or metastatic UC is treated with chemotherapy. In the UK, cisplatin-based chemotherapy is offered. If cisplatin-based chemotherapy is unsuitable, carboplatin in combination with gemcitabine is offered among Programmed death-ligand 1 (PD-L1) negative patients, and atezolizumab or carboplatin in combination with gemcitabine is offered for PD-L1 positive patients. 2L treatment depends on prior treatment and includes platinum-based chemotherapy, checkpoint inhibitors or BSC (7,8).

In June 2020, the FDA approved avelumab for maintenance treatment in patients with locally advanced or metastatic UC that have not progressed with 1L platinum-containing chemotherapy (9). In January 2021, the European Commission (EC) approved avelumab as a monotherapy for the 1L maintenance treatment of adult patients with locally advanced or metastatic UC who are progression-free following platinum-based chemotherapy (10). Avelumab is a human monoclonal Immunoglobulin G1 (IgG1) antibody that targets the immunomodulatory cell surface ligand protein, PD-L1. The JB100 trial was designed to be a randomized, multicentre and open label study conducted to understand the efficacy of avelumab. Maintenance therapy with avelumab in addition to BSC showed improved overall survival compared to BSC alone in patients with advanced UC whose cancer had not progressed following 1L platinum-based chemotherapy (11,12). Overall survival at 1 year was 71% in the avelumab group and 58% in the control group, with a hazard ratio for death reported at 0.69 (95% confidence interval, CI, 0.56 – 0.86, p=0.001). Median overall survival was 21.4 months in the avelumab group vs. 14.3 months in the control group and median progression

free survival was 3.7 months vs. 2.0 months, respectively. Patients received avelumab following a treatment-free interval of four to ten weeks after receipt of four to six cycles of chemotherapy with gemcitabine plus cisplatin or carboplatin. AEs of any grade occurred in 98.0% of patients in the avelumab group and 77.7% in the control group (13).

This NIS aims to understand clinical outcomes of patients treated with avelumab as monotherapy for the 1L maintenance treatment of locally advanced or metastatic UC who are progression-free following platinum-based chemotherapy, in a real-world setting in the UK.

8. RESEARCH QUESTION AND OBJECTIVES

The purpose of this NIS is to describe the early clinical real-world outcomes of patients treated with avelumab as monotherapy for the 1L maintenance treatment of locally advanced or metastatic UC who are progression-free following platinum-based chemotherapy. As from September 2020, patients in the UK meeting the UC indication have been provided access to avelumab via EAMS. This study aims to investigate patients who received avelumab in secondary/tertiary care in the UK through either the EAMS or through NHS commissioning. The primary objective of this study is to compare overall real-world survival with overall survival reported by the JB100 clinical trial (13). Detailed objectives have been ratified by three NHS medical oncologists with an academic interest in UC to ensure feasibility in the real-world setting, are as follows:

Among all adult patients with locally advanced or metastatic UC who are progression-free following platinum-based chemotherapy and are treated with avelumab as a 1L maintenance therapy:

Primary Objective

1. To estimate rwOS in a real-world cohort of patients treated with maintenance avelumab for locally advanced or metastatic UC

Secondary objectives

1. To describe the demographic and clinical characteristics of this cohort at first diagnosis of UC, diagnosis of locally advanced or metastatic disease and at avelumab treatment initiation
2. To estimate real-world rwPFS from initiation of avelumab
3. To describe treatment characteristics of the anti-cancer therapies received for locally advanced or metastatic UC **prior** to the initiation of avelumab as a 1L maintenance therapy
4. To describe treatment patterns **after** initiation of avelumab as a 1L maintenance therapy

5. To describe the AEs explicitly attributed to avelumab in a real-world population
6. To describe real-world all-cause associated healthcare resource burden associated with avelumab therapy

9. RESEARCH METHODS

9.1. Study design

This is a multi-centre, UK-based, NIS, with both a retrospective chart review and prospective follow-up of patients. Data collected as part of routine care entered into electronic patient records and paper-based charts will be extracted from records of adult patients with locally advanced or metastatic UC whose disease has not progressed following 1L platinum-based chemotherapy, and are treated with avelumab as a 1L maintenance therapy. Detailed information on the setting, the inclusion and exclusion criteria of patients, the study period and follow-up are described below.

The primary outcome of interest is rwOS and secondary outcomes include rwPFS and rwTTD. Other variables of interest include demographic, clinical and treatment characteristics. Outcome and variable definitions are described in detail in section 9.

This is a NIS because there will be no patient contact and only clinical data collected in routine clinical care will be collected and analysed as part of this study. No study visits, examinations, laboratory tests or procedures will be mandated. No changes to routine patient management are expected to occur as a result of a patient's inclusion in the study.

[figure not shown]

Figure 1. Schematic of the study design

9.1.1. Setting

This study is to be conducted in secondary/tertiary care centres of the UK NHS. In the UK, avelumab is indicated as monotherapy for the 1L maintenance treatment of adult patients with locally advanced or metastatic UC who are progression-free following platinum-based chemotherapy.

The study aims to recruit approximately 100 patients treated with avelumab with follow-up for up to 24 months after avelumab initiation. Among all centres who have registered patients as treated with avelumab, we will select 8-12 centres for participation ensuring a good geographical spread and instruct centres to extract data from 6-12 patients per centre. Potential participating hospitals will be subject to a site feasibility assessment to ensure eligible sites have the required number of patients, access to data and capacity to take part in this study. Data collection will commence after the appropriate ethics and research and development (R&D) approvals have been obtained and the site is fully initiated.

Centres will be provided with clear instructions on how to identify patients and extract their data. They will be instructed to extract patients in chronological order of avelumab initiation (earliest first) to avoid selection bias and to ensure consistency in the recruitment methodology across the participating research sites. Centres will be requested to recruit 6-12 patients each so that the geographical spread of patients across centres is maintained.

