9.1.2. Inclusion criteria

Patients must meet all the following inclusion criteria to be eligible for inclusion in the study:

1. Patients with a diagnosis of locally advanced or metastatic UC, either de novo or relapsed
2. Patients received 1L platinum-based chemotherapy and had stable disease, partial response, or complete response to this treatment
3. Patients received avelumab as indicated as a monotherapy for the first-line maintenance treatment of adult patients with locally advanced or metastatic UC who are progression-free following platinum-based chemotherapy
4. Patients aged ≥ 18 years on the date that they commenced avelumab

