9.1.4. Study period

The data collection period will start November 2021 with retrospective identification of patients first treated with avelumab since September 2020. It is anticipated that by July 2021 fewer than 100 patients will have been treated with avelumab in the UK across NHS sites participating in this study. Therefore, the patient identification window and subsequent follow up window would need to be extended by prospective identification of patients up to the time point the 100th patient is entered. After identification of all patients, periodic data collection of treatment and outcome data for all identified patients will run until 24 months has elapsed since the avelumab initiation date for each patient, with the data collection component of the study being completed shortly after 24 months since the latest initiation date in the study.

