*In June 2020, the FDA approved avelumab for maintenance treatment in patients with locally advanced or metastatic UC that have not progressed with 1L platinum-containing chemotherapy (9). In January 2021, the European Commission (EC) approved avelumab as a monotherapy for the 1L maintenance treatment of adult patients with locally advanced or metastatic UC who are progression-free following platinum-based chemotherapy (10). Avelumab is a human monoclonal Immunoglobulin G1 (IgG1) antibody that targets the immunomodulatory cell surface ligand protein, PD-L1. The JB100 trial was designed to be a randomized, multicentre and open label study conducted to understand the efficacy of maintenance avelumab. Maintenance therapy with avelumab in addition to BSC showed improved overall survival compared to BSC alone in patients with advanced UC whose cancer had not progressed following 1L*

PFIZER CONFIDENTIAL

CT24-WI-GL03-RF03 0.2 *Non-Interventional Statistical Analysis Plan For Secondary Data Collection*  
*Study 01-Jun-2020*  
*Page 10 of 34*

*platinum-based chemotherapy (11,12). Overall survival at 1 year was 71% in the avelumab group and 58% in the control group, with a hazard ratio for death reported at 0.69 (95% confidence interval, CI, 0.56 – 0.86,  $p=0.001$ ). Median overall survival was 21.4 months in the avelumab group vs. 14.3 months in the control group and median progression-free survival was 3.7 months vs. 2.0 months, respectively. Patients received avelumab following a treatment-free interval of four to ten weeks after receipt of four to six cycles of chemotherapy with gemcitabine plus cisplatin or carboplatin. AEs of any grade occurred in 98.0% of patients in the avelumab group and 77.7% in the control group (13).*

*This NIS aims to understand clinical outcomes of patients treated with avelumab as monotherapy for the 1L maintenance treatment of locally advanced or metastatic UC who are progression-free following platinum-based chemotherapy, in a real-world setting in the UK.*

PFIZER CONFIDENTIAL

CT24-WI-GL03-RF03 0.2 *Non-Interventional Statistical Analysis Plan For Secondary Data Collection*  
*Study 01-Jun-2020*  
*Page 11 of 34*

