Type of SACT regimen received as 1L therapy before avelumab start date	Treatment patterns	From date of locally advanced or metastatic diagnosis to index date	Type of 1L SACT regimen received after date of locally advanced or metastatic diagnosis date until index date, inclusive, as recorded in eCRF Q28: 
 
• Cisplatin/gemcitabine
 
• MVAC (Methotrexate, vinblastine, doxorubicin and cisplatin) in combination with granulocyte-colony stimulating factor (G-CSF)
 
• Carboplatin/gemcitabine
 
• Other cisplatin regimen
 
• Other carboplatin regimen
 

Number of SACT cycles received as 1L therapy before avelumab start date	Treatment patterns	From date of locally advanced or metastatic diagnosis to index date	Number of SACT cycles received as 1L therapy before avelumab start date, as recorded in eCRF Q28 (1-8 cycles)
Number of patients switching between different platinum-based chemotherapies	Treatment patterns	From date of locally advanced or metastatic diagnosis to index date	If there is any evidence of patients changing regimens during 1L therapy prior to avelumab, as reported in eCRF Q29 (yes/no/not recorded)
Time duration between completion date of 1L SACT and start date of avelumab	Treatment patterns	From date of the last record of 1L SACT to avelumab initiation date	Calculated as the number of days from the end date of the last 1L SACT cycle (eCRF Q28) to the start date of avelumab (eCRF Q25), inclusive of the start and end dates of this period.
Response to 1L SACT before avelumab start date	Treatment patterns	From date of 1L SACT initiation to date of avelumab initiation	Response to 1L SACT as reported in eCRF Q29: 
 
• Complete response
 
• Partial response
 

PFIZER CONFIDENTIAL

			
 
• Stable disease
 

Response to 1L SACT based on CT scan after 1L SACT and before avelumab	Treatment patterns	From date of 1L SACT initiation to date of avelumab initiation	If response to 1L SACT was judged based on CT scan evidence after the last cycle of 1L SACT, as reported in eCRF Q29 (yes/no)
Objective 5: to describe treatment patterns after avelumab initiation (table shell Table 2.4.1 and 2.4.2 and Figure 2.2)			

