## **10.5 STUDY LIMITATIONS**

### **Selection bias**

Selection bias could be introduced to the study via patient selection methods, since the study population is small and only includes participants from EAMS and EAMS extension NHS sites, which could differ demographically from NHS sites more generally. These patient selection methods are necessary to find sufficient numbers of patients using avelumab therapy. Given that the date for the EMA license for avelumab is 30th June 2020, low numbers of patients are expected to be using it, therefore the sample size for this study is limited to the first 100 eligible patients.

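### Survival is to be compared with a trial that started avelumab 4–10 weeks after chemotherapy, but the collected gap enters no survival output, so the effect of any delayed starters on rwOS and rwPFS would not be visible

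*Protocol*

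**What the plan says.** **Sampling.** The identification window opens with "retrospective identification of patients first treated with avelumab since September 2020" (Protocol 9.1.4), the month in which early access began. Protocol 9.1.1 will "instruct centres to extract data from 6-12 patients per centre", and says of the order: "They will be instructed to extract patients in chronological order of avelumab initiation (earliest first) to avoid selection bias". SAP 10.5 adds that "the sample size for this study is limited to the first 100 eligible patients".

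**Eligibility.** The chemotherapy criterion reads: "Patients received 1L platinum-based chemotherapy and had stable disease, partial response, or complete response to this treatment" (Protocol 9.1.2). The SAP version requires the response to be recorded before avelumab starts. Neither list sets a minimum or maximum gap between the last chemotherapy cycle and avelumab.

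**Reference trial.** Protocol 8 and SAP 5 both state an aim to compare the cohort's overall survival with that reported for JB100. In that trial: "Patients received avelumab following a treatment-free interval of four to ten weeks" (SAP 4; also Protocol 7).

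**Use of the gap.** SAP 8 derives it: "Calculated as the number of days from the end date of the last 1L SACT cycle (eCRF Q28) to the start date of avelumab", counting both end dates. It is summarised as a treatment characteristic. SAP 10.1 sends every objective to a single full analysis set. SAP 10.2 and 10.3 estimate rwOS and rwPFS once each, with no split or restriction by gap.

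**Limitations.** Protocol 9.8 and SAP 10.5 cover site selection, data quality, treatment duration, under-recorded adverse events and length of follow-up. They do not mention selection of patients during the interval before avelumab.

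**The concern.** Both survival clocks start at avelumab initiation. A patient who starts late has already remained alive and progression-free through an untreated interval that is not counted. If patients differ in underlying risk, those still eligible after a long interval will tend to be the lower-risk ones.

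When a maintenance drug first becomes available, a centre's first users may include such patients. Taking the earliest starters guards against a centre choosing favourable cases, but it also weights the sample towards the period in which delayed starts are most plausible.

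The comparison with JB100 is what is at stake. A cohort containing patients with gaps outside 4–10 weeks is not like for like with that trial, and the planned outputs would not show how much of any difference came from this. Protocol 10.2 already takes the risk of a survivor cohort seriously, since it is one ground for not seeking consent. The gap before avelumab is another possible route to the same problem.

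**Working it through.** **1. The plan's own precision (Protocol 9.4, Table 5, 100 patients).** Clopper-Pearson limits:
- 71/100 at 12 months: 61.1% to 79.6% (stated 61–80%).
- 48/100 at 24 months: 37.9% to 58.2% (stated 38–58%).

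Table 5 reproduces. The half-width at 24 months is about 10 points.

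**2. How concentrated the sample is.** 8 × 6 = 48 to 12 × 12 = 144 patients. Starts run from September 2020 to about June 2022, taking the June 2024 end of data collection less 24 months, so about 21 months. The earliest-first cap per centre concentrates any initial backlog, and the long window dilutes it. The documents do not show which dominates.

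**3. Illustrative effect on 24-month rwOS.** Let *f* be the share of delayed starters and *d* their survival advantage at 24 months over the planned 48%. Then shift = *f* × *d*. Both inputs are assumptions.
- *f* = 0.10, *d* = 0.10: 1 point.
- *f* = 0.30, *d* = 0.20: 6 points.

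**4. The same on a hazard scale.** With hazard ratio *h* for death in delayed starters, cohort survival = (1 − *f*) × 0.48 + *f* × 0.48^*h*. Again *f* and *h* are assumed.
- *f* = 0.10, *h* = 0.8: 0.9 × 0.48 + 0.1 × 0.556 = 48.8%.
- *f* = 0.30, *h* = 0.7: 0.7 × 0.48 + 0.3 × 0.598 = 51.5%. This is above 50%, so the median would not be reached within 24 months, against 21.4 months in JB100.
- *f* = 0.50, *h* = 0.5: 0.5 × 0.48 + 0.5 × 0.693 = 58.6%.
- *h* = 1: 48.0%, no change.

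**5. What rwPFS shows about the condition for bias.** Take JB100 median PFS of 3.7 months on avelumab and 2.0 months in the control arm, and a gamma frailty with variance *v* (assumed). The untreated rate is λ = (2^*v* − 1)/(*v* × 2.0). After *g* extra progression-free months off treatment, median PFS from avelumab is 3.7 × (1 + *v*λ*g*). With *g* = 3:
- *v* = 0 (all patients at the same constant risk): 3.7 months, no bias at all.
- *v* = 0.5: λ = 0.414, median 3.7 × 1.621 = 6.0 months; a cohort with 30% such patients has median 4.3.
- *v* = 1: λ = 0.5, median 3.7 × 2.5 = 9.25 months; the 30% mixture has median 4.9.

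The upward shift therefore comes from differences in risk between patients, not from waiting as such.

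**6. The window in days.** 4 × 7 = 28 and 10 × 7 = 70 elapsed days. SAP 8 counts both end dates, so the same window is 29–71 in its derived variable.

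**7. Cost in precision.** If 70 of 100 patients fell in the window (assumed), the approximate half-width at 24 months is 1.96 × √(0.48 × 0.52/70) = 0.117, about ±12 points.

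**The case against.** The strongest case against is that the selection is conjectural. Neither document reports a backlog or a distribution of gaps. The terms of early access are not given, so they may themselves have limited the interval. The study is also meant to describe early users, treated "through either the EAMS or through NHS commissioning", and delayed starters, if any, belong to that population. SAP 6.2 says no formal comparison is planned. The gap will already be reported with mean, median, quartiles, minimum and maximum (SAP 10.3), so a sizeable delayed group would be seen. A subset overlapping the FAS cannot statistically resolve a shift of 1–6 points.

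Most of this stands, and it limits the point to a conditional one. It does not remove it. The gap summary would show that delayed starters exist, but not what they do to survival. The JB100 comparison is a stated aim even without a test.

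Three stronger readings do not hold:
- A reader might infer that the cohort is enriched and its survival overstated. The documents support only that this is possible.
- A reader might use the control-arm median PFS of 2.0 months to gauge bias. On an exponential curve, 1 − 0.5^(1.38/2.0) = 38% progress or die between weeks 10 and 16, and 1 − 0.5^(3.68/2.0) = 72% between weeks 10 and 26. These figures describe depletion. An exponential curve with one common rate has no memory, so it implies zero bias. Heavy depletion would also leave fewer patients able to start late.
- A reader might split the cohort at 21 January 2021 to separate early access from commissioning. Protocol 9.8.1 says an early-access extension followed that date, so the split would mislabel patients. Nor does SAP 10.5 make a claim about commissioned patients that would need limiting.

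**Conclusion.** The point holds in conditional form. The plan intends a comparison with a trial that had a defined 4–10 week gap, sets no such limit itself, samples the earliest starters, and leaves the gap out of every survival output. Upward bias in rwOS and rwPFS relative to JB100 requires both that delayed starters are present and that progression or death risk varies between patients.

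The size is unknown. The 1–6 point range at 24 months rests wholly on the assumed 10–30% share and 10–20 point advantage. The wider assumptions in step 4 (10–50% delayed, hazard ratio 0.5–0.8) give 0.8 to 10.6 points. If few patients start late, the effect is negligible. As a plain description of early UK users the estimate remains valid, and the weakness lies in reading it against JB100.

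**What to change.** Leave the sampling rule, eligibility and FAS unchanged.

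- **SAP 10.2 and 10.3:** add a sensitivity estimate of rwOS and rwPFS in patients whose gap is 4–10 weeks, defined as 28–70 elapsed days (29–71 in the SAP's inclusive count). Report the numbers of patients below and above the window. The window is chosen only to match JB100 and implies nothing about when treatment should start.
- **SAP 10.5:** state that patients may be selected by remaining progression-free during the interval before avelumab, that earliest-first sampling does not prevent this, and that comparison with JB100 should be read alongside the 4–10 week estimate.

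The cost is SAP wording and a small addition to the outputs, using dates already collected. The subset will have a wider interval, about ±12 points at 24 months if 70 patients qualify, so it serves as a like-for-like check and not as a test of whether the gap matters.
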